**Theta-Burst Neuromodulation for PTSD (TBS)** ClinicalTrials.gov Identifier: NCT02769312 Version: August 17, 2017

Participants: 55 adult Veterans, ages 18-70 with current PTSD will participate in study procedures.

*Inclusion criteria:* Principle inclusion criteria will be diagnosis of chronic PTSD, meeting DSM-5 criteria. Eligible male and female Veterans will be between ages 18-70, and, if in treatment, symptomatic despite ongoing stable treatment regimens for at least 6 weeks prior to study procedures. Ongoing medications and psychotherapy will be allowed to continue unchanged during the study. Veterans must also be willing and able to comply with all study related procedures and visits, and capable of independently reading and understanding patient information materials and providing informed consent.

*Exclusion criteria:* For safety, participants must meet established screening criteria safety during MRI, which is implemented as a conservative measure given the novel application of TBS in this population, since MRI involves magnetic fields at similar intensity to those emitted from the stimulation coil. These measures require a patient not having the following (unless MRI-safe): Cardiac pacemaker, implanted device (deep brain stimulation) or metal in the brain, cervical spinal cord, or upper thoracic spinal cord. TMS-specific exclusions are pregnancy/lactation, or planning to become pregnant during the study, lifetime history of moderate or severe traumatic brain injury (TBI), current unstable medical conditions, current (or past if appropriate) significant neurological disorder, or lifetime history of a) seizure disorder b) primary or secondary CNS tumors c) stroke or d) cerebral aneurysm. Other exclusions are any primary psychotic disorder, bipolar I disorder, active moderate/severe substance use disorders (within the last month, excluding nicotine/caffeine, assessed with urine drug testing), have active suicidal intent or plan as detected on screening instruments or in the investigative team's judgment is likely to attempt suicide within 6 months, and other conditions or circumstance that, in the opinion of the investigator team, has the potential to prevent study completion and/or to have a confounding effect on outcome assessments.

## **Procedures and Symptom Measures**

Following eligibility determination, participants will be randomized to either active or sham TBS, using urn randomization (Wei & Lachin, 1988) with PTSD symptom severity, mild TBI, sex, and depression diagnosis (yes/no) as blocking variables.

*Visit Schedule and TBS Procedures.* Veterans will attend 10 TBS/sham sessions, delivered over 10 consecutive business days. Each session will last approximately 10 minutes. 10 unblinded sessions will be offered after the double blind phase. Veterans will return to the PVAMC one month later for a post-treatment follow assessment to durability of changes observed. All stimulation will be performed with a Magstim Super Rapid2+1 stimulator equipped with a double 70mm biphasic figure-of-eight air-cooled coil, available at PVAMC. Following established procedures for TBS (Huang et al., 2005) iTBS "dose" will be determined based on each Veteran's active motor threshold (AMT). AMT will be determined using standard procedures. The stimulator coil will then be placed tangentially to the scalp with the handle pointing posteriorly. Stimulation will be applied over the hand area of the right motor cortex (M1) and localized for each participant based on the optimal position to elicit MEPs in the contralateral FDI.

Once the AMT has been determined, the coil will be placed over the right DLPFC using the Beam Method (Beam et al., 2009), and active TBS will be delivered at 80% of AMT (Li et al., 2014). iTBS parameters will include stimulation of three pulses at 50 Hz, given every 200 ms (5 times per second). Two-second trains of these stimulations will be repeated every 10 seconds for a total of 1800 pulses (delivered over 570 seconds)(Li et al., 2014). Sham procedures will be identical, except will use the Magstim sham coil. Medications and therapy will be held stable to the extent possible during study participation, and changes in treatment during iTBS will be recorded.

*Participant Safety*. Safety will be assessed at every TBS session by recording spontaneously reported adverse events, and participants will be queried daily about potential side effects associated with TBS such as seizure, headache and dizziness. A licensed physician with experience in both neuromodulation and PTSD will be available at all times during study procedures and all participants will be required to wear hearing protection.

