## DATA ANALYSIS

**Feasibility and Acceptability.** Feasibility will be evaluated by rates of recruitment, treatment adherence, retention and completion of assessments. Acceptability will be measured by retention and participant reports of acceptability and satisfaction. To determine the feasibility and acceptability of TBS, we will examine rates of session attendance (as a proxy for adherence to TBS procedures), dropouts, completion of assessments, number and severity of adverse events, qualitative exit interviews and satisfaction ratings. Feasibility and acceptability of the sham control will use the same procedures as well as assessment of the quality of the sham as indicated above. We will consider 75% session attendance and satisfaction rates of 70% participants as the minimum indicator of acceptability, and completion of a minimum of 75% of end of treatment and 1-month follow up assessments to reflect feasibility. Based on prior use of TBS for depression, we expect fewer than 5% of participants to experience an adverse event, and those that do occur will match the known profile of TBS.

**Data Analysis for RCT.** Random assignment of participants with regard to baseline characteristics to TBS and sham groups will be initially assessed. We will include as covariates *a priori* specified variables that are plausibly important for explaining the outcome (i.e., baseline PTSD, depression symptom severity and quality of life) and potentially differentially distributed by random assignment. We will also evaluate the degree to which Veterans report changes in other treatments during the intervention to ensure observed changes are related to TBS. Preliminary data analysis will calculate rates of dropout, distributional properties of dependent and other variables, and differences between those subjects who agree and decline to participate.

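### Does the mismatch between the stated 570 s delivery time and the other stimulation figures call for a change to the plan?

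*Combined protocol and SAP*

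**What the plan says.** The stimulation pattern is described once, under Visit Schedule and TBS Procedures in the Procedures and Symptom Measures section. Bursts are specified as "stimulation of three pulses at 50 Hz, given every 200 ms (5 times per second"). The next sentence gives the train length, the repeat interval, the pulse total and the delivery time: "Two-second trains of these stimulations will be repeated every 10 seconds for a total of 1800 pulses (delivered over 570 seconds"). The same section describes the visit in round terms: "Each session will last approximately 10 minutes". For the control arm it states: "Sham procedures will be identical, except will use the Magstim sham coil".

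In the DATA ANALYSIS section, adherence is measured by "rates of session attendance (as a proxy for adherence to TBS procedures"). The minimum standards there are 75% session attendance, a 70% satisfaction rate, and completion of 75% of the end-of-treatment and 1-month assessments. The primary analysis is a mixed model of CAPS/PCL and QLESQ/SOFAS scores over time.

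**The concern.** Six figures describe one series of pulses: pulses per burst, burst rate, train length, repeat interval, pulse total and delivery time. Any five of them fix the sixth, and the sixth as printed does not match. The sentence specifies the intervention and nothing else in the documents describes the pattern, so a reader cannot settle the conflict by looking elsewhere.

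If the mismatch reached the delivered treatment, more would be at stake. A shortfall in pulses, or a different pattern in the two arms, would make it unclear what the trial had tested. Someone checking the device settings, or repeating the trial, could not meet the pulse total, the interval and the duration together.

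**Working it through.** **Inputs, all from Procedures and Symptom Measures**
- 3 pulses per burst
- 5 bursts per second (one every 200 ms; 20 ms between pulses at 50 Hz)
- trains of 2 s
- one train every 10 s
- 1800 pulses in total
- stated delivery time 570 s

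**Can 570 s be reproduced?**
- Pulses per train: 3 × 5 × 2 = 30
- Trains needed: 1800 / 30 = 60
- Start of the 60th train: 59 × 10 = 590 s
- Last single pulse: 590 + 9 × 0.2 + 2 × 0.02 = 591.84 s
- End of the 60th train: 590 + 2 = 592 s (check: 60 × 2 s on + 59 × 8 s off = 120 + 472 = 592 s)
- With the closing rest: 60 × 10 = 600 s

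It cannot. Even the start of the last train falls 20 s after the stated end. To the end of the last train the gap is 592 − 570 = 22 s, and 22/592 = 3.7%. Over full cycles it is 600 − 570 = 30 s, and 30/600 = 5.0%.

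**Other readings**

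| Reading | Result |
|---|---|
| 10 s is the pause between trains (12 s cycle) | 59 × 12 + 2 = 710 s, further away |
| 10 s is a rounded interval, one even series | needs (570 − 2)/59 = 9.63 s, or 570/60 = 9.5 s with the closing rest |
| Three back-to-back blocks of 20 trains, no rest at the joins | 3 × (19 × 10 + 2) = 576 s |
| The same blocks, each timed only to the start of its last train | 3 × 190 = 570 s |

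An interval of 9.63 s would be printed as 10 in whole seconds, but the text does not say that the figure is rounded. The block readings rest on a structure that the protocol does not describe. Either might explain where 570 s came from. Neither makes the text consistent as printed.

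**Does anything depend on the duration?**
- *Delivery.* Burst, train, interval and pulse total define the series without the duration.
- *Session length.* In minutes, 570, 592 and 600 s are 9.5, 9.9 and 10.0, and all of them fit a session of about 10 minutes.
- *Comparison of arms.* Sham differs only in the coil, so the same figures apply to both arms.
- *Feasibility and acceptability.* The thresholds concern attendance, satisfaction and completed assessments. None uses seconds of stimulation.
- *Efficacy.* The outcomes are symptom, quality-of-life and function scores. Neither the models nor the covariates include duration.

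**The case for a change.** The best case for acting is that a protocol should specify its intervention without contradiction, and this one does not. The figures are given as exact values, the cited source cannot mend figures that disagree on the page, and checking the device program would lead to a one-line correction. A harder version says that 570 s at one train every 10 s has room for only 57 trains, which is 57 × 30 = 1710 pulses, or 90 pulses (5%) below the stated total.

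The first part stands as a remark on the text: the figures disagree and must be reconciled. The harder version does not stand. It lets the duration in parentheses override the pulse total in the same sentence, and nothing in the protocol supports that order of priority. No loss of pulses can be inferred. Even on that reading, the shared procedure would put both arms on the same schedule, so the randomised comparison would stay fair.

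**Conclusion.** The inconsistency is genuine: 570 s is 22 to 30 s (3.7% to 5.0%) shorter than the time implied by 60 trains at one every 10 s. It is clerical, and no change to the design or analysis follows. The sponsor has to reconcile the pulse total, the interval and the delivery time. The documents do not show which is off, and no view is taken here. Whatever the answer, the randomisation, the 55 participants, the outcomes, the thresholds and the models stay as they are, and so does what the trial can conclude.

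This rests on two assumptions. One is that the device settings are the same for every session and both arms, as the sham statement implies. The other is that adherence is judged by attendance, as the DATA ANALYSIS section says, and not by time under stimulation.

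### Adverse-event collection is described only at TBS sessions and no reporting window is set, so the adverse-event count may be incomplete after a participant's last session

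*Combined protocol and SAP*

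**What the plan says.** Safety collection is described once, in the Participant Safety paragraph of *Procedures and Symptom Measures*: "Safety will be assessed at every TBS session by recording spontaneously reported adverse events, and participants will be queried daily about potential side effects". Its first half ties recording to sessions, and its second half adds an active query. No start or end date is given for that query.

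The Visit Schedule paragraph of the same section sets the calendar. For the blinded phase, "Veterans will attend 10 TBS/sham sessions, delivered over 10 consecutive business days". Then, "10 unblinded sessions will be offered after the double blind phase". For follow-up, "Veterans will return to the PVAMC one month later for a post-treatment follow assessment to durability of changes observed". Durability is the only purpose given for that visit.

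*Measures and Participant Assessments* lists instruments by domain. None is an adverse-event or side-effect measure.

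In *DATA ANALYSIS*, the Feasibility and Acceptability paragraph examines, besides session attendance, "dropouts, completion of assessments, number and severity of adverse events, qualitative exit interviews and satisfaction ratings", and applies the same procedures to the sham control. It expects under 5% of participants to have an adverse event, with no time window. Its numeric criteria are 75% session attendance, 70% satisfaction, and 75% completion of end-of-treatment and 1-month assessments.

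**The concern.** An event that follows one session can be picked up at the next. An event that follows a participant's last session has no described point of capture. This affects three situations: a completer after the final session, a participant who stops early (possibly because of a side effect), and the follow-up month.

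Two things are at stake. First, the plan will test whether benefit is sustained to 1 month, while the tolerability data it describes stop at the last session. Second, the count has no fixed observation period. Those who accept the optional unblinded sessions are observed for longer than those who decline, and a count without a stated window can mix blinded and unblinded exposure.

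**Working it through.** The plan derives no adverse-event figure, so there is nothing to reproduce. Three checks can be made.

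**1. Share of days spanned by sessions**

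Inputs from the plan: 10 blinded sessions on 10 consecutive business days, 10 optional unblinded sessions, and a follow-up visit one month later. Assumptions: a month is 30 days, and the unblinded sessions follow directly on business days.

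- 10 business days span 12 calendar days with a Monday start, and otherwise 14. 20 business days span 26 to 28.
- Share = session span ÷ (days from first session to the 1-month visit).

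| Participant | Month runs from | Share of days |
|---|---|---|
| Blinded sessions only | last blinded session | 12/(12+30) = 12/42 = 29%; 14/(14+30) = 14/44 = 32% |
| Blinded and unblinded | last unblinded session | 26/(26+30) = 26/56 = 46%; 28/(28+30) = 28/58 = 48% |
| Blinded and unblinded | last blinded session | 26/42 = 62%; 28/44 = 64% |

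The plan does not say which session the month is counted from, hence the range of 46–64% for those who take the unblinded sessions.

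**2. What the 5% expectation means as a count**

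0.05 × 55 = 2.75, so under 5% means at most 2 participants: 2/55 = 3.6% and 3/55 = 5.5%. One participant decides on which side the result falls. This takes all 55 as the denominator. The plan does not say whether the expectation is for both arms together or for active TBS alone.

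**3. Illustration of incomplete capture**

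Let *p* be the true share of participants with an adverse event and *c* the share of those participants who are recorded. The number recorded is taken as binomial(55, *p* × *c*). Both *p* and *c* are assumptions; the plan gives neither. The table shows the chance of recording 3 or more affected participants, that is, of seeing the expectation exceeded.

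| True rate *p* | *c* = 100% | *c* = 90% | *c* = 75% | *c* = 50% |
|---|---|---|---|---|
| 5% | 52% | 45% | 34% | 16% |
| 8% | 83% | 77% | 65% | 38% |
| 10% | 92% | 88% | 79% | 52% |

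With a true rate of 8%, for example, missing a quarter of affected participants lowers the chance of seeing the expectation exceeded from 83% to 65%. This shows sensitivity only. It does not estimate what this trial would miss.

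**The case against.** The strongest reply is that the plan is silent on later collection but does not exclude it. The document is short, and the daily query has no stated end, so session days are the likelier reading but not the only one. A reader might infer that late events are missed and that the count is too low. The documents do not support that: they give no rate of late events, and the undercount may be zero.

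Other parts of the reply also stand:

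- A reader might take the 68–71% of days outside sessions (30/44 to 30/42) as the size of the loss. It applies only to those who decline the unblinded sessions, and a share of days is not a share of events. Side effects of stimulation may well cluster near sessions.
- A reader might infer that worsening after stimulation would go unseen. *Measures and Participant Assessments* has CAPS-5 repeated after TBS and at the end of follow-up, so worsening of PTSD would show as scores, though the plan does not call it an adverse event.
- A reader might infer that the feasibility and acceptability verdict is at risk. None of the three numeric criteria uses adverse events, and the 5% figure is an expectation with no pass/fail role.
- Dropouts are counted and exit interviews are held. Either might bring events to light, but the plan does not say that they record them.
- Suicidal intent is screened for through unspecified instruments or the team's judgment. No particular question is identified that could simply be repeated later.

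These points limit the claim but do not close the gap. Followed as written, the plan gives staff no instruction to ask about adverse events once a participant's sessions end, and it does not say what period the count covers.

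**Conclusion.** The concern holds as a risk of incomplete collection and an undefined reporting window; it is not a demonstrated undercount. The only collection described is at TBS sessions, with a daily query of unstated duration. Nothing is described after the last session, at the 1-month visit, or for early stoppers.

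The span of days covered differs between participants: about 29–32% with blinded sessions only, and about 46–64% with unblinded sessions as well. These figures rest on a 30-day month, on unblinded sessions that follow directly, and on either reading of when the month starts.

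What is exposed is the descriptive safety summary and its comparison with the 5% expectation, where the line falls between 2 and 3 of 55 participants. The attendance, satisfaction and completion criteria are unaffected. The change is still worth making, because it alters what the trial collects, costs little, and gives the tolerability data the same time span as the test of sustained benefit.

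**What to change.** Amend Participant Safety so that the same adverse-event recording and side-effect query, identical in both arms, is also done:

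- at the end-of-treatment assessment, if it is separate from the last session;
- at the 1-month visit;
- at last contact for anyone who stops early.

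State when the daily query ends and from which session the month is counted. In Feasibility and Acceptability, define the adverse-event count as running from first session to the 1-month visit, with blinded, unblinded and follow-up periods shown separately, and say whether the 5% expectation refers to all participants or to active TBS, and over which period.

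The cost is a few minutes at visits already planned, a brief contact for early stoppers, and one more table. The reported adverse-event rate may come out slightly higher.

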## **Measures and Participant Assessments**

*Diagnostic/Screening:* Age, demographics, race, education, current treatments and psychopharmacologic medication history will be recorded. SCID-5 - The Structured Clinical Interview for DSM-5 (First, 2014) will be used to establish psychiatric diagnoses, current and lifetime, and inclusion/exclusion criteria.

PTSD: CAPS-5 – The Clinician Administered PTSD Scale (Weathers et al., 2013a) will be used to establish a PTSD diagnosis at baseline, and change in scores over time will capture symptom change after TBS and at the end of the follow up period. PCL-5 – The PTSD Checklist (Weathers et al., 2013b) is a 20-item self-report scale of PTSD symptoms. LEC-5 – The Life Event Checklist (Weathers et al., 2013c) assesses for lifetime trauma exposure.

Mood, Affect and Anxiety: IDS-SR – the Inventory of Depressive Symptoms, Self Report (Rush et al., 2003) is a self-report scale that provides a continuous measure of depression severity. PANAS – The Positive and Negative Affect Schedule (Watson et al., 1988) will evaluate changes in affective status. STAI – The State-Trait Anxiety Scale (Spielberger et al., 1983) will evaluate changes in anxiety outside of PTSD symptoms. Quality of Life, Function and Sleep: QLESQ-SF – The 18-item Quality of Life Enjoyment and Satisfaction Questionnaire (Ritsner et al., 2005) evaluate QOL and other areas of change related to functioning outside of symptom domains. SOFAS – The Social and Occupational Functioning Scale (Morosini et al., 2000) will evaluate changes in functional status attributable to study procedures. PSQI – The Pittsburgh Sleep Quality Index (Buysse et al., 1989) will assess changes in quality of sleep.

*General:* CGI – The clinical global impressions of severity and improvement (Guy, 1978) will be used to capture overall symptom severity and improvement associated with treatment.

Treatment Satisfaction – The treatment satisfaction form (Blatt et al., 1998) will gather feedback from participants related to study participation.

*Blinding*: At double blind endpoint Veterans will be queried as to whether they received active or sham.

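### No side-effect query before stimulation and no new-or-worsened rule are described, so pre-existing headache or dizziness can raise the absolute adverse-event rate in both arms

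*Combined protocol and SAP*

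**What the plan says.** The combined protocol and SAP describes two sources of safety data, both during treatment (Procedures and Symptom Measures, Participant Safety). The first is spontaneous: "Safety will be assessed at every TBS session by recording spontaneously reported adverse events". The second is solicited: "participants will be queried daily about potential side effects associated with TBS such as seizure, headache and dizziness". The double-blind course is fixed: "Veterans will attend 10 TBS/sham sessions, delivered over 10 consecutive business days". Ten unblinded sessions are offered afterwards.

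For the pre-treatment record, Measures and Participant Assessments states: "Age, demographics, race, education, current treatments and psychopharmacologic medication history will be recorded". It adds a psychiatric interview and the symptom, function and sleep scales. Headache and dizziness are not named. The eligibility criteria exclude moderate or severe TBI and significant neurological disorder. Mild TBI is evidently admitted, because randomization runs "with PTSD symptom severity, mild TBI, sex, and depression diagnosis (yes/no) as blocking variables".

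DATA ANALYSIS, Feasibility and Acceptability, lists among the measures to be examined the "number and severity of adverse events, qualitative exit interviews and satisfaction ratings". It applies the same procedures to sham and expects under 5% of participants to have an adverse event, of a kind that fits what is already known of TBS. The plan does not define an adverse event, say whether a yes to the daily query becomes one, or say whether the query comes before or after that day's stimulation.

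**The concern.** Headache and dizziness are common complaints that can exist before treatment, and a sample that admits mild TBI plausibly includes some Veterans who have them. A Veteran with a habitual complaint who is asked on 10 treatment days will probably say yes at least once. Without a pre-treatment answer to the same question, the analyst cannot tell a long-standing complaint from one that began or worsened under stimulation.

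The type of symptom does not help, because the query itself names headache and dizziness as effects of TBS. A habitual headache would therefore look like part of the expected profile. Severity has the same difficulty: worsening cannot be shown without a starting level.

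At stake is the reading of the absolute count and severity in each arm, which the plan uses to describe the feasibility and acceptability of TBS and of sham. The unblinded sessions are more exposed, since no concurrent sham is described there. A baseline that was not collected cannot be collected prospectively once stimulation has begun.

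**Working it through.** **Inputs from the plan.** N = 55 (opening section: "55 adult Veterans, ages 18-70 with current PTSD will participate in study procedures"), 10 blinded sessions, and an expected adverse-event rate under 5% of participants. No split between arms is given.

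**Assumed inputs.** p is the share of Veterans with a habitual complaint who say yes at least once during the course. t is the true treatment-related rate. Neither is in the plan. I take p from 0% to 20% and t = 4%, just inside the expectation.

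**Step 1: the plan's figure as a count.** The 5% comes from prior use of TBS in depression and has no derivation to reproduce. 0.05 × 55 = 2.75, so under 5% means at most 2 of 55 (2/55 = 3.6%). Three of 55 is already 5.5%.

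**Step 2: no effect of stimulation, every habitual complaint counted.** The expected count is 55p: 2.75 at 5%, 5.5 at 10% and 11 at 20%. That is about 3 to 11 Veterans.

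**Step 3: with t = 4% added.** The share counted is q = 1 − (1 − p)(1 − t), taking the two sources as independent. The chance of 3 or more of 55 is binomial. For simplicity t is applied to all 55, so these rows overstate the treatment part for anyone on sham. The last column is the active-minus-sham difference when p is equal in both arms and t applies to active only: q − p = t(1 − p).

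| p | q | Expected of 55 | P(3 or more) | Active − sham, points |
|---|---|---|---|---|
| 0% | 4.0% | 2.2 | 0.38 | 4.0 |
| 5% | 8.8% | 4.8 | 0.87 | 3.8 |
| 10% | 13.6% | 7.5 | 0.985 | 3.6 |
| 20% | 23.2% | 12.8 | about 1.00 | 3.2 |

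The absolute rate moves a great deal with p. The difference between arms shrinks slightly. Even at p = 0 there is a 0.38 chance of passing the expected level, so exceeding it would not by itself show a counting problem.

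**Step 4: why a calculation by independent days is the wrong model.** If every Veteran had the same daily chance d of a complaint, independent between days, the chance of at least one yes in 10 queries would be 1 − (1 − d)^10. For d = 1%, 2%, 5% and 10% this is 9.6%, 18.3%, 40.1% and 65.1%, or 5.3, 10.1, 22.1 and 35.8 of 55. But this describes sporadic complaints spread over everyone. Habitual complaints cluster in the same people: if 10% of person-days came from 10% of Veterans with daily symptoms, 5.5 of 55 would be affected, not 35.8.

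Under the independent-day model a baseline would not cure the problem either. The chance of a clear two-week look-back is (1 − d)^14 = 0.87, 0.75, 0.49 and 0.23. The false counts left are 55 × (1 − d)^14 × [1 − (1 − d)^10] = 4.6, 7.6, 10.8 and 8.2. I therefore rest the size on Step 2.

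**The case against.** The strongest answer is that the sham arm already does this work. Procedures are identical except for the coil, the same query is put to both arms, and mild TBI is one of the urn factors, so background complaints are expected equally on both sides. This stands for the comparison: a reader might infer that TBS would look worse than sham because of habitual headache, and the last column of the table shows the opposite, a slight dilution. It does not repair the absolute rate in each arm, which the plan also uses, nor the unblinded sessions.

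Second, the plan keeps spontaneous adverse events and queried side effects as two items and nowhere says that the second feeds the first. That also stands. A reader might infer that habitual headache is counted and that the number is inflated. The documents support only that this can happen, since the counting rule is unstated. If only spontaneous reports count, the query has no stated analytic use, and habitual complaints mentioned unprompted are still unclassified.

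Third, no decision turns on the count. The stated minima are 75% attendance, 70% satisfaction and 75% completion of assessments; the 5% is an expectation. This limits the weight of the point.

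Fourth, the screening list may not be exhaustive, since eligibility requires some neurological and medical history. The session 1 query would also serve as a baseline if asked before stimulation, and staff could ask at a first yes whether the complaint is usual. So it would be too strong to say that the information is bound to be lost. But none of this is written, and recall after treatment starts is a weaker source than a prospective answer.

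**Conclusion.** The point holds in limited form. No pre-stimulation side-effect query and no new-or-worsened rule are described, so pre-existing headache or dizziness can enter the adverse-event count and raise the absolute rate in both arms and in the unblinded sessions. With 5% to 20% of Veterans having habitual complaints, about 3 to 11 of 55 could be counted with no effect of stimulation, against at most 2 of 55 under the plan's expectation. This assumes that queried complaints are counted and that each such Veteran says yes at least once; the background rate is not in the documents.

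The documents do not support three stronger readings: that inflation is certain, that the contrast between arms is biased against TBS, or that the trial could fail a criterion because of it. Larger figures, up to about 36 of 55, belong to the independent-day model and do not describe habitual complaints. The efficacy analyses are untouched. This is a worthwhile and inexpensive improvement to the reading of tolerability, not a threat to the main conclusions.

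**What to change.** In Procedures and Symptom Measures, Participant Safety: administer the same side-effect questions once before any stimulation, that is, before motor-threshold testing, and record frequency and worst severity.

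In DATA ANALYSIS, Feasibility and Acceptability: state whether queried complaints enter the adverse-event count. Count a queried complaint only if it is new, or more frequent or more severe than at that baseline. Report solicited events, spontaneous events and pre-existing complaints separately by arm.

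The cost is one form, a few minutes at an existing visit and a short addition to the analysis text. One limit remains: sporadic or under-reported complaints that are absent at baseline will still count as new. The rates in the blinded phase should therefore be read alongside the sham rate even after the change.
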